## **10.0 Confidentiality and Privacy**

Confidentiality will be protected by collecting only information needed to assess study outcomes, minimizing to the fullest extent possible the collection of any information that could directly identify subjects, and maintaining all study information in a secure manner. To help ensure subject privacy and confidentiality, only a unique study identifier will appear on the data collection form. Any collected patient identifying information corresponding to the unique study identifier will be maintained on a linkage file, stored separately from the data. The linkage file will be kept secure, with access limited to designated study personnel. Following data collection subject identifying information will be destroyed (state the anticipated time the data will be destroyed, e.g. three years after closure of the study, and the method of destruction), consistent with data validation and study design, producing an anonymous analytical data set. Data access will be limited to study staff. Data and records will be kept locked and secured, with any computer data password protected. No reference to any individual participant will appear in reports, presentations, or publications that may arise from the study.

## **11.0 Data Safety and Monitoring**

The principal investigator will be responsible for the overall monitoring of the data and safety of study participants. The principal investigator will be assisted by other members of the study staff.

## **12.0 Reporting of Unanticipated Problems, Adverse Events or Deviations**

Any unanticipated problems, serious and unexpected adverse events, deviations or protocol changes will be promptly reported by the principal investigator or designated member of the research team to the IRB and sponsor or appropriate government agency if appropriate.

## 13.0 Adverse Events List and Reporting Requirements

### 13.1 Adverse Event List for Propranolol

Cardiovascular: Bradycardia; congestive heart failure; intensification of AV block; hypotension; paresthesia of hands; thrombocytopenic purpura; arterial insufficiency, usually of the Raynaud type.

Central Nervous System: Light-headedness, mental depression manifested by insomnia, lassitude, weakness, fatigue; catatonia; visual disturbances; hallucinations; vivid dreams; an acute reversible syndrome characterized by disorientation for time and place, short-term memory loss, emotional lability, slightly clouded sensorium, and decreased performance on neuropsychometrics. For immediate-release formulations, fatigue, lethargy, and vivid dreams appear dose-related.

Gastrointestinal: Nausea, vomiting, epigastric distress, abdominal cramping, diarrhea, constipation, mesenteric arterial thrombosis, ischemic colitis.

Allergic: Hypersensitivity reactions, including anaphylactic/anaphylactoid reactions, pharyngitis and agranulocytosis; erythematous rash, fever combined with aching and sore throat; laryngospasm, and respiratory distress.

Respiratory: Bronchospasm.

Hematologic: Agranulocytosis, nonthrombocytopenic purpura, thrombocytopenic purpura.

Autoimmune: Systemic lupus erythematosus (SLE).

Skin and mucous membranes: Stevens-Johnson Syndrome, toxic epidermal necrolysis, dry eyes, exfoliative dermatitis, erythema multiforme, urticaria, alopecia, SLE-like reactions, and psoriasisiform rashes. Oculomucocutaneous syndrome involving the skin, serous membranes and conjunctivae reported for a beta blocker (practolol) have not been associated with propranolol.

Genitourinary: Male impotence; Peyronie's disease.

### 13.2 Adverse Event Characteristics

- **CTCAE term (AE description) and grade:** The descriptions and grading scales found in the revised NCI Common Terminology Criteria for Adverse Events (CTCAE) version 4.0 will be utilized for AE reporting. All appropriate treatment areas should have access to a copy of the CTCAE version 4.0. A copy of the CTCAE version 4.0 can be downloaded from the CTEP web site (<http://ctep.cancer.gov>).

- **'Expectedness'**: AEs can be 'Unexpected' or 'Expected' (see Section 7.1 above) for expedited reporting purposes only.
- **Attribution** of the AE:
  - Definite – The AE is **clearly related** to the study treatment.
  - Probable – The AE is **likely related** to the study treatment.
  - Possible – The AE **may be related** to the study treatment.
  - Unlikely – The AE is **doubtfully related** to the study treatment.
  - Unrelated – The AE is **clearly NOT related** to the study treatment.

### **13.3 DSMC SAE Reporting Requirements**

The Data and Safety Monitoring Committee (DSMC) is responsible for reviewing SAEs for WFBCCC Institutional studies as outlined in Appendix F. DSMC currently requires that all unexpected 4 and all grade 5 SAEs on these trials be reported to them for review. All WFBCCC Clinical Research Management (CRM) staff members assisting a Principal Investigator in investigating, documenting and reporting an SAE qualifying for DSMC reporting are responsible for informing a clinical member of the DSMC as well as the entire committee via the email notification procedure of the occurrence of an SAE.

### **13.4 WFBH IRB AE Reporting Requirements**

Any unanticipated problems involving risks to subjects or others and adverse events shall be promptly reported to the IRB, according to institutional policy. Reporting to the IRB is required regardless of the funding source, study sponsor, or whether the event involves an investigational or marketed drug, biologic or device. Reportable events are not limited to physical injury, but include psychological, economic and social harm. Reportable events may arise as a result of drugs, biological agents, devices, procedures or other interventions, or as a result of questionnaires, surveys, observations or other interactions with research subjects.

All members of the research team are responsible for the appropriate reporting to the IRB and other applicable parties of unanticipated problems involving risk to subjects or others. The Principal Investigator, however, is ultimately responsible for ensuring the prompt reporting of unanticipated problems involving risk to subjects or others to the IRB. The Principal Investigator is also responsible for ensuring that all reported unanticipated risks to subjects and others which they receive are reviewed to determine whether the report represents a change in the risks and/or benefits to study participants, and whether any changes in the informed consent, protocol or other study-related documents are required.

Any unanticipated problems involving risks to subjects or others occurring at a site where the study has been approved by the WFBH IRB (internal events) must be reported to the WFBH IRB within 7 calendar days of the investigator or other members of the study team becoming aware of the event.

Any unanticipated problems involving risks to subjects or others occurring at another site conducting the same study that has been approved by the WFBH IRB (external events) must be reported to the WFBH IRB within 7 calendar days of the investigator or other members of the study team becoming aware of the event.

Any event, incident, experience, or outcome that alters the risk versus potential benefit of the research and as a result warrants a substantive change in the research protocol or informed consent process/document in order to insure the safety, rights or welfare of research subjects.

## **14.0 Pharmaceutical Information**

A list of the adverse events and potential risks associated with the investigational or commercial agents administered in this study can be found in Section 12.1.

### **14.1 Pharmaceutical Accountability**

Propranolol will be provided by the study as per section 5.0.

### **14.2 Propranolol**

**Product description:** Propranolol hydrochloride is a stable, white, crystalline solid available in 10, 20, 40, 60 and 80 mg tablets. For this study, 40 mg tablets will be used.

**Solution preparation:** NA

**Storage requirements:** Store at room temperature. Protect from light

**Stability:** Propranolol is stable.

**Route of administration:** Take by mouth 2 hours before prostate biopsy

**Disposal:** Dispose of any unused tablets in line with local and institutional regulations.

## Appendix A – Subject Eligibility Checklist

IRB Protocol No. 00043227	WFCCC Protocol No. 8 5 7 1 6
Study Title: Evaluating the effect of the ADRB2 blockers on PKA/BAD/CREB signaling in the prostate gland	
Principal Investigator: [name]., [name], D.V.M, Ph.D.	

Inclusion Criteria (as outlined in study protocol)	Criteria is met	Criteria is NOT met	Source Used to Confirm * (Please document dates and lab results)
Men > 18 years of age			
Patients undergoing prostate biopsy or prostatectomy			
Individuals able to understand and willing to sign an IRB-approved informed consent document			
Exclusion Criteria (as outlined in study protocol)	Criteria NOT present	Criteria is present	Source Used to Confirm * (Please document dates and lab results)
Men taking propranolol daily for any reason are excluded			
Men with baseline SBP <120 or HR <63			
Men unable to swallow pills			
History of current or past medical or psychiatric illness that would make participation difficult or not feasible at the discretion of the principal investigator or co-investigators			

This subject is  eligible /  ineligible for participation in this study.

WISER Assigned PID: \_\_\_\_\_

Signature of research professional confirming eligibility: \_\_\_\_\_

Date: \_\_\_\_\_

Signature of Treating Physician\*\*: \_\_\_\_\_

Date: \_\_\_\_\_

\* Examples of source documents include clinic note, pathology report, laboratory results, etc. When listing the source, specifically state which document in the medical record was used to assess eligibility. Also include the date on the document. Example: "Pathology report, 01/01/14" or "Clinic note, 01/01/14"

\*\*Principal Investigator signature can be obtained following registration if needed

## Appendix B – Protocol Registration Form

### DEMOGRAPHICS

Patient: Last Name: \_\_\_\_\_ First Name: \_\_\_\_\_

MRN: \_\_\_\_\_ DOB (mm/dd/yy): \_\_\_\_\_ / \_\_\_\_\_ / \_\_\_\_\_

ZIPCODE: \_\_\_\_\_

Ethnicity (choose one):  Hispanic  
 Non-Hispanic

Race (choose all that apply):  WHITE  BLACK  ASIAN  
 PACIFIC ISLANDER  NATIVE AMERICAN

Primary Diagnosis: \_\_\_\_\_

Date of Diagnosis: \_\_\_\_\_ / \_\_\_\_\_ / \_\_\_\_\_

### Randomization

This patient has been randomly assigned to the following treatment arm (Check one):

\_\_\_\_\_ Propranolol and Prostate biopsy or prostatectomy (Group 1)

\_\_\_\_\_ Prostate biopsy or prostatectomy only (Group 2)

Randomization Recorded by: \_\_\_\_\_ Date \_\_\_\_\_ / \_\_\_\_\_ / \_\_\_\_\_ Time \_\_\_\_\_

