## **3.0 Study Population**

Patients recruited will be individuals scheduled for prostate biopsy or prostatectomy. For this study, 60 individuals will be recruited. Patients will be randomized to receive the treatment (or not) for a total of 30 patients receiving propranolol prior to biopsy or prostatectomy and 30 patients receiving no treatment. It is expected that approximately 10 (5 patients in each group) may have non-evaluable tumor tissue. In case the number of evaluable tumors will be less than 25 for each group, more patients will be recruited to accumulate 25 evaluable samples for each group.

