#### Contact Information:

Protocol Registrar [contact]

Protocol Registrar [contact]

Protocol Registrar E-MAIL ([[contact]](mailto:[contact]))

\*Protocol Registration is open from 8:30 AM - 4:00 PM, Monday-Friday.

4. Fax/e-mail ALL eligibility source documents with registration. Patients **will not** be registered without all required supporting documents.

Note: If labs were performed at an outside institution, provide a printout of the results. Ensure that the most recent lab values are sent.

To complete the registration process, the Registrar will:

- assign a patient study number
- Randomized Group Assignment
- register the patient on the study

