#### **4.2 Methods**

#### **Compare activation of ADRB2/PKA/BAD signaling pathway in the prostate glands of men who take or do not take ADRB2-selective beta blockers**

##### **Patients scheduled for prostate biopsy.**

The research staff screens the OR and clinic schedules for potential patients and provides a list to the investigator. [name] or co-Investigator will discuss the study with the patient and inform the research nurse or coordinator (research staff) about the patients who agreed to participate in the study. Research staff will inform Tissue Procurement Lab (Director [name]; [name], Tumor Procurement Coordinator) and courier about the scheduled date and time when prostate samples will be collected.

On the day of sample collection [name] lab will prepare box with dry ice for prostate biopsy samples, a box with wet ice for blood samples as well as 2 ml cryovials (Corning, cat#430488) to collect biopsies and tubes to collect blood (Na heparin, green-capped tube, 10 ml total blood volume).

Courier will pick up boxes from Tissue Procurement Lab (Director [name]; [name], [contact]) and deliver to research staff at Charlois clinic ([name]).

Recruited patients scheduled for prostate biopsy will be randomized into two groups. Group one will receive 40 mg propranolol given by research nurse 2 hours prior to prostate biopsy. The research nurse should withhold drug and contact treating physician if SBP <120 or HR < 63. Group two will receive no treatment.

All patients will fill out stress surveys on the biopsy day.

All patients will give approximately 10 mL of blood approximately 20 min prior to prostate biopsy to test plasma catecholamine levels (collected in 10 mL green top tube (sodium heparin) and sent on ice within 1 hour to clinical lab for processing) and propranolol level (collected in 10 mL green top tube (sodium heparin) and sent on ice to The Tissue Procurement lab for processing and storage as described below). For group one that takes propranolol, this blood sample will be drawn at 1.5 -2 hours after taking the propranolol tablet.

For the biopsy, at least 1 core of the prostate specimen is to be flash frozen (on dry ice -80C) for laboratory analysis. Each biopsy sample will be collected into separate cryovials. The samples will be picked up by courier at Charlois clinic and delivered to Tissue Procurement laboratory.. The tissue samples will be frozen at -80 C.

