### **Patients scheduled for prostatectomy.**

Research staff will inform Tissue Procurement Lab (Director [name]; [name], Tumor Procurement Coordinator) about the scheduled date and time when samples from prostate cancer patients will be collected at OR. Prior to the day of sample collection at specified time [name] lab will provide vials and freezing media to collect prostatectomy samples and plasma samples (Na heparin, green cup).

Recruited patients scheduled for prostatectomy will be randomized into two groups. Group one will receive 40 mg propranolol given by research staff 2 hours prior to prostatectomy. The research staff should withhold drug and contact the study physician performing the procedure and/or the anesthesiologist if SBP <120 or HR < 63. Group two will receive no treatment. All patients will fill out stress surveys prior to prostatectomy.

Research staff will collect stress questionnaire and will collect blood into the vials with Na heparin that will be stored on ice (+4C). All patients will give approximately 10 ml of blood approximately 20 min prior to prostatectomy to test plasma catecholamine levels and propranolol level. For group one that takes propranolol, this blood sample will be drawn at 1.5 -2 hours after taking the propranolol tablet. Blood will be collected into two 10 mL green top (sodium heparin) tubes. One tube will sent on ice within 1 hour to the clinical lab for processing of fractionated catecholamines. The other tube will be sent on ice to The Tissue Procurement lab for processing and storage. The plasma will be separated, transferred to cryovials, and stored in -80C at the Tissue Procurement Lab

Prior to anesthesia patient will be evaluated by anesthesiologist for hypotension and bradycardia. Prostatectomy samples will be collected by Tissue Procurement Coordinator and placed into cryovials and flash-frozen. At least 3 vials with the prostate specimens will be flash frozen (on dry ice -80C) for laboratory analysis and stored at the Tissue Procurement Lab.

Prostate samples will be analyzed for the overall status of prostate tissue (by pathologist) and for activation of ADRB2/PKA signaling pathway .

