## Appendix H – Tissue Collection

### TISSUE COLLECTION FORM

This form is for the collection of core samples of prostate tissue.

**Sample Handling:** Tubes used for collecting sample should be labelled with the patient study number (Patient ID), initials and date. Samples should be frozen in liquid nitrogen and stored in the Tumor Tissue Core at -80 until use.

Tumor Tissue Core  
Wake Forest Baptist Comprehensive Cancer Center  
Tumor Tissue Core Facility  
Care of [name]  
[name]  
[name]  
[name]

**WISER PID:** \_\_\_\_\_ **Date Completed:** \_\_\_\_ / \_\_\_\_ / \_\_\_\_

**PI:** [name]., [name], D.V.M., Ph.D.

**Study Number:** CCCW FU 85716

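### The plan does not say whether randomisation is stratified by procedure, no readable form codes biopsy versus prostatectomy, and the primary t-test ignores it

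*Combined protocol and SAP*

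**What the plan says.** **Allocation.** Section 4.2 (Methods) treats the two pathways in turn. For biopsy it says "Recruited patients scheduled for prostate biopsy will be randomized into two groups"; for prostatectomy, "Recruited patients scheduled for prostatectomy will be randomized into two groups". Section 3.0 gives one total over both procedures: "for a total of 30 patients receiving propranolol prior to biopsy or prostatectomy and 30 patients receiving no treatment". In section 4.1 the registrar's task is listed only as "Randomized Group Assignment". The document does not mention strata, blocks or how the list is made.

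**Forms.** The Randomization part of Appendix B offers two arm labels, "Propranolol and Prostate biopsy or prostatectomy (Group 1" and "Prostate biopsy or prostatectomy only (Group 2", with no box for which procedure. Appendix A has one merged criterion, "Patients undergoing prostate biopsy or prostatectomy", and a free-text source column. Appendix H is headed "This form is for the collection of core samples of prostate tissue", although section 4.2 also sends prostatectomy specimens for freezing. The surgery-type entry in Appendix G belongs to prior therapy. Appendices I and N show no procedure field. The bodies of Appendices J to M were not readable in the text available to me.

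**Analysis.** Section 8.2 compares mean CREB phosphorylation (pCREB) between arms by a two-sample t-test with no procedure term.

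**The concern.** Procedure could plausibly affect the primary outcome. Section 4.2 describes different settings and specimens: at least one core, couriered from a clinic, for biopsy; at least three vials collected at the operating room, with an anaesthetic assessment beforehand, for prostatectomy. The planning mean and SD in section 8.1 come from a biopsy study, so the document gives no pCREB value for prostatectomy tissue.

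With 60 men, an allocation that ignores procedure can easily leave the arms with different procedure mixes. Whatever the allocation, an unadjusted test leaves any between-procedure variation in the error term. Stratification has to be settled before men are allocated. A coded field is the simplest way to support both stratified assignment and an adjusted analysis.

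**Working it through.** **Inputs from the document:** SD 0.26, target difference 0.21, control mean 0.73, 25 evaluable per arm, two-sided alpha 0.05 (section 8.1); 60 men, 30 per arm (section 3.0).

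**Assumptions, because the document gives neither figure:** a prostatectomy share of 20 to 50%; a mean pCREB difference between procedures of 0.13 to 0.26 (0.5 to 1 SD). I take 0.26 as the within-procedure SD, since it comes from biopsies.

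**1. The plan's own power.** Effect size 0.21/0.26 = 0.81; relative change 0.21/0.73 = 29%. The noncentral t with 25 per arm gives 79.9%. The stated 80% reproduces.

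**2. Chance imbalance if allocation is unstratified.** With K prostatectomy men among 60 and 30 per arm, the number X in one arm is hypergeometric (60, K, 30), and the arms differ by |2X − K| men.

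| Assumed share | K | P(arms differ by 6 or more) |
|---|---|---|
| 20% | 12 | 0.104 |
| 25% | 15 | 0.072 |
| 30% | 18 | 0.158 |
| 40% | 24 | 0.187 |
| 50% | 30 | 0.196 |

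The dip at 25% arises because K is odd, so the difference must be odd and six or more means seven or more. At 50%, the chance of eight or more is 0.070.

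**3. Effect on the arm difference.** Shift = procedure difference × 6/30.
- 0.13 × 0.2 = 0.026, and 0.026/0.21 = 12% of the target.
- 0.26 × 0.2 = 0.052, and 0.052/0.21 = 25% of the target.

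The standard error of the arm difference is 0.26 × √(2/25) = 0.074, so these shifts are about 0.35 and 0.7 standard errors.

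**4. Power of the unadjusted test at an even mix.** Total SD = √(0.26² + 0.5 × 0.5 × d²), where d is the procedure difference.
- d = 0.13: SD 0.268, power 77%.
- d = 0.26: SD 0.291, power 71%.
- With procedure in the model the residual SD returns to 0.26 and power to about 80%, at the cost of one degree of freedom.
- d = 0: no loss.

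At a 20% share the same formula gives 78% and 74%.

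**5. Stratifying but keeping the unadjusted t-test.** Balance removes the procedure component from the true variance of the arm difference, but the t-test still estimates its error from the total SD. The test becomes conservative: in simulation the type I error is about 4.4% (d = 0.13) or 3.0% (d = 0.26) instead of 5%. Stratification and adjustment therefore belong together.

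**The case against.** The strongest reply is that there is no established defect. Unstratified randomisation is unbiased, chance imbalance is already covered by the error rate of the t-test, and stratifying a 60-man pilot is a design preference. All of that stands. The size also rests on a procedure mix and a procedure effect that the document does not give.

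Three stronger readings are tempting, and the document supports none of them.

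- *Section 4.2 specifies separate lists, which Appendix B contradicts.* The two sentences may only describe parallel pathways. Neither names strata, blocks or lists, and a 30/30 total is compatible with either method.
- *Appendix B assigns from one undivided pool.* The form records an assignment that the registrar has already made. The registrar must also receive all eligibility source documents, which probably reveal the procedure. A stratified list would produce the same form.
- *Procedure never reaches the database, so an imbalance could be neither seen nor corrected.* Section 9 sends Appendices J to M to REDCap, and I could not read their bodies. Appendix B carries the record number, section 10 keeps a linkage file, and section 4.2 already plans retrospective chart extraction. Procedure can be recovered.

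What survives is narrower: the allocation method is not stated, no readable form codes procedure, and the planned analysis does not use it.

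**Conclusion.** The point holds as a gap in specification with a nearly costless remedy. It is not a proven error in allocation and not a source of bias. If allocation is unstratified, an imbalance of six or more prostatectomy men has a probability of about 7 to 20% at the shares tabulated. Such an imbalance shifts the estimate by 0.026 to 0.052, up or down, if the procedure difference is 0.13 to 0.26.

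The more dependable gain comes from the analysis: at an even mix, putting procedure in the model recovers roughly 2 to 9 percentage points of power. If procedure does not affect pCREB, neither the shift nor the loss of power arises. I would label this a cheap improvement.

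**What to change.** 1. **Appendix B:** add a coded item, Procedure: biopsy / prostatectomy, completed before the arm is assigned.
2. **Section 4.1:** state that the registrar assigns 1:1 from two permuted-block lists, one per procedure, and how the lists are generated. If a stratified list is already in use, say so. Align sections 3.0 and 4.2 with that wording.
3. **Data:** carry the field into REDCap with the pCREB results. First check whether Appendices J to M already hold it.
4. **Section 8.2:** replace the unadjusted t-test with a linear model of pCREB on arm and procedure, reporting the adjusted arm difference with its 95% confidence interval. This also deals with imbalance that arises after allocation, when the 60 randomised men fall to about 50 evaluable; stratified lists cannot control that loss.

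The cost is one extra list, one form and database field, and one degree of freedom. The sample size and what patients undergo do not change. Items 1 and 2 work only for men not yet allocated. For men already enrolled, procedure can be taken from the chart and item 4 still applies, provided the model is fixed before pCREB is compared between arms.
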